3.1.3. Study Endpoints

The PK endpoints will include modeled PK parameters such as apparent systemic clearance (CL/F), apparent volume of distribution (V/F), and area under the concentration-time curve (AUC) for edoxaban and metabolites, and metabolite/parent ratios for AUC.

The PD endpoints will include observed, change-from-baseline, and percent-change-from-baseline PT, aPTT, and anti-FXa.

Safety assessments will include: AEs, physical examination findings, vital signs, standard hematology, clinical chemistry, and urinalysis laboratory tests. Note: urinalysis will be performed with plastic bags with a sticky strip from neonates and infants with diapers.

Palatability of the liquid formulation will be assessed using visual analog scale (VAS) scores.

3.1.4. Duration of the Study

The first patient is expected to be enrolled in June 2014.

3.1.5. Duration of Patient Participation

Approximately 4 weeks for each patient, which will include a screening period (within 21 days of dosing), a treatment period, and a follow-up visit conducted within 10 days after dosing. However, a patient will be considered to have completed the study if they provide the last scheduled PK sample. The treatment period will consist of predose procedures occurring on Day -1 or 1, dosing on Day 1, and postdose procedures occurring postdose on Days 1, 2 (all cohorts) and Day 3 (all patients enrolled prior to Version 5.0 of the protocol may have had Day 3 PK samples obtained). The treatment period days may occur as in-patient or out-patient based on the clinic's ability/discretion. The overnight stays are not mandatory. Check-out procedures will be performed after the last PK/PD blood samples are collected.

3.1.6. Stopping Rules

Due to potential tolerability differences among age cohorts, stopping criteria will be applied independently to each age cohort. The minimum intolerable dose will be defined as (1) the dose

at which a minimum of 60% of evaluable patients in an age cohort experiences more than 1 occurrence of moderate or severe AEs, related to edoxaban or (2) the dose at which at least 1 patient in an age cohort experiences an SAE judged to be medically serious and related to edoxaban as assessed by an independent DSMB. The DSMB will be responsible for reviewing and assessing the available safety data as set forth in the DSMB Charter.

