3. STUDY DESIGN

3.1. Overall Plan

3.1.1. Study Type

This is a Phase 1, open-label, single-dose, non-randomized, multiple-center PK and PD study in pediatric patients. The study will include 5 pediatric age cohorts with evaluation of 2 different doses within each age cohort (low- and high-dose).

Age cohorts and dose groups:

- 12 to < 18 years of age on the day of dosing (12 evaluable total patients)
 - Cohort 1a: Low-dose group (6 patients)
 - Cohort 1b: High-dose group (6 patients)
- 6 to < 12 years of age on the day of dosing (12 evaluable total patients)
 - Cohort 2a: Low-dose group (6 patients)
 - Cohort 2b: High-dose group (6 patients)
- 2 to < 6 years of age on the day of dosing (12 evaluable total patients)
 - Cohort 3a: Low-dose group (6 patients)
 - Cohort 3b: High-dose group (6 patients)
- 6 months to < 2 years of age on the day of dosing (12 evaluable total patients)
 - Cohort 4a: Low-dose group (6 patients)
 - Cohort 4b: High-dose group (6 patients)
- 38 weeks gestation to < 6 months of age on the day of dosing (12 evaluable total patients)
 - Cohort 5a: Low-dose group (6 patients)
 - Cohort 5b: High-dose group (6 patients)

A total of 60 patients will be enrolled such that 12 evaluable patients will be in each age cohort and 6 patients will be within each dose group. Dropouts or patients with unusable data (for reasons other than AEs) may be replaced.

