3.1.2. Treatment Groups

Patients will be dosed orally with a single dose of edoxaban on Day 1. Patients in the 12 to < 18 years of age cohort will be dosed with multiples of edoxaban tablets of 30 mg strength. Patients younger than 12 years of age will receive the edoxaban granule for oral suspension. The dosing amount and formulation type may change based on emerging data.

If a patient is unable or unwilling to ingest the assigned dosing form (tablet or suspension formulation), the patient will not be enrolled and will be replaced.

Patients will be administered edoxaban in the morning with water.

- Cohorts 1a/1b: 120 mL water;
- Cohorts 2a/2b: 60 mL water;
- Cohorts 3a/3b: 40 mL water;
- Cohorts 4a/4b: 10 mL water;
- Cohorts 5a/5b: 10 mL water.

Patients will be asked to fast for at least 4 hours before dosing and for an additional 2 hours after dosing. If this is not feasible because of the patient's age or other needs, (unflavored) milk, or an equivalent substitute liquid (but not fruit juices), will be allowed until 1 hour before and starting at 1 hour postdose. During this period, the total volume of liquids should not exceed 240 mL, excluding the volume of water utilized for dosing.

Order of enrollment will be from the oldest age cohort to the youngest age cohort. Within each age cohort, enrollment will first start in the lower dose group (to achieve exposures comparable to a 30 mg adult dose). After evaluation of PK and safety data from at least half the patients in the lower dose group, enrollment may then start in the higher dose group (to achieve exposures comparable to a 60 mg adult dose). If the observed exposures are higher than expected in the lower dose group and exceed the projected 60 mg adult exposure, then a lower dose may be investigated in the proposed "high-dose" group. Enrollment in the next younger age cohorts will begin when at least 50% of patients have completed the study in the older age cohort.

Enrollment in the younger age cohorts will start only after PK and safety data have been evaluated from at least 6 patients (3 low-dose and 3 high-dose) in the older age cohort.

Pharmacokinetic and safety data will be reviewed by a DSMB (see Section 11.9) who will approve the start of the next younger age cohort. However, enrollment initiation of Cohort 5 may be considered without PK and safety data from at least 50% of patients in the preceding older dose group.

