5.1.1. Method of Assigning Patients to Treatments and Blinding

This will be an open-label study. This study is not randomized. Patients will receive edoxaban on 1 occasion. Enrollment will first start in the lower dose group of the oldest age cohort (to achieve exposures comparable to a 30 mg adult dose). After evaluation of PK and safety data from at least half the patients in the lower dose group, enrollment will start in the higher dose group (to achieve exposures comparable to a 60 mg adult dose). If the observed exposures are higher than expected in the lower dose group and exceed the projected 60 mg adult exposure then a lower dose may be investigated in the proposed “high-dose” group. Enrollment in the next younger age cohorts will begin when PK and safety data from at least 50% (N = 6) of patients in the preceding older dose group have been reviewed. Pharmacokinetic and safety data will be reviewed by a DSMB (see Section 11.9) who will approve the start of the next younger age cohort. However, enrollment initiation of Cohort 5 may be considered without PK and safety data from at least 50% of patients in the preceding older dose group. An attempt will be made to enroll patients spanning the entire age range for each age cohort.

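### Two safety thresholds do not match the patients they refer to: Section 5.1.1 calls 6 patients half of a 6-patient dose group, and stopping criterion (1) judges a dose but words its 60% over an age cohort of two doses

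*Combined protocol and SAP*

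**What the plan says.** **Planned numbers.** Section 3.1.1 plans that "12 evaluable patients will be in each age cohort and 6 patients will be within each dose group". Section 5.1.1 adds: "Patients will receive edoxaban on 1 occasion". Each patient therefore contributes to one dose only.

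**Opening the next younger cohort.** Section 5.1.1 makes this depend on PK and safety data from "at least 50% (N = 6) of patients in the preceding older dose group have been reviewed". The Synopsis (Study Design) and Section 3.1.2 instead state the 50% over the older age cohort. They add that younger cohorts start only once data from at least six patients of that cohort, three at each dose, have been evaluated. All three places then allow Cohort 5 to be considered without data from at least half of the preceding dose group.

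**Stopping criteria.** Section 3.1.6 says that "stopping criteria will be applied independently to each age cohort". For criterion (1), the minimum intolerable dose is one "at which a minimum of 60% of evaluable patients in an age cohort experiences more than 1 occurrence of moderate or severe AEs", where the events are related to edoxaban. Criterion (2) names "the dose at which at least 1 patient in an age cohort experiences an SAE judged to be medically serious". Such an event must also be drug-related in the DSMB's assessment. The DSMB is responsible for "reviewing and assessing the available safety data as set forth in the DSMB Charter".

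**Escalation within a cohort.** Under Section 3.1.2 the higher dose group may open "After evaluation of PK and safety data from at least half the patients in the lower dose group".

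**The concern.** Both passages set a safety decision threshold as a percentage, and in both the base of the percentage does not fit the planned numbers.

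In Section 5.1.1 the stated percentage, the stated count and the stated unit cannot all be true. Read alone, the section could be satisfied by six patients who all received the same dose, which the Synopsis and Section 3.1.2 do not allow. The same unit appears in the exception for Cohort 5, the youngest patients, where it decides how much evidence may be waived.

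In Section 3.1.6 the thing judged is a dose, but the patients named as the base are those of an age cohort, which holds two doses. Criterion (1) is the protocol's only numerical rule for related moderate or severe events that are not serious. Depending on the base, the same six affected patients at one dose either exceed the threshold or fall short of it.

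**Working it through.** **Inputs.** 12 evaluable patients per age cohort and 6 per dose group (Section 3.1.1); two doses per cohort (Section 3.1.1); one dose per patient (Section 5.1.1); stopping threshold 60% (Section 3.1.6); cohort-opening threshold 50% with N = 6 (Section 5.1.1). No event rates are assumed.

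**(a) Cohort opening: the plan's own figure first.**

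- Base as worded, a dose group: 0.50 × 6 = 3 patients, and 6/6 = 100%. The stated 50% with N = 6 does not reproduce.
- Base as in the Synopsis and Section 3.1.2, an age cohort: 0.50 × 12 = 6 patients, and 6/12 = 50%. The stated figure reproduces.

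The count therefore belongs to the age cohort and the word naming the unit does not. On the dose split, the Synopsis and Section 3.1.2 require 3 + 3 = 6, while Section 5.1.1 gives 6 without a split.

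Cohort 5 exception: half of a dose group is 0.50 × 6 = 3 patients; half of an age cohort is 0.50 × 12 = 6. The wording gives the first. The second follows if the unit slip in Section 5.1.1 is carried over. Because the exception directly follows the cohort-opening conditions, the requirement of three patients per dose is not unconditional for Cohort 5.

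**(b) Stopping criterion (1).** The smallest number of affected patients that meets the rule is 0.60 × base, rounded up.

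| Reading | Base | Needed | Can one dose meet it alone? |
|---|---|---|---|
| Age cohort as scope; patients at that dose counted | 6 | 0.60 × 6 = 3.6, so 4 (4/6 = 66.7%) | Yes |
| Literal cohort base; numerator from the dose judged | 12 | 0.60 × 12 = 7.2, so 8 | No: maximum 6/12 = 50% |
| Both doses pooled in numerator and base | 12 | 8 (8/12 = 66.7%) | No: each dose must supply at least 8 − 6 = 2 |

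On the pooled reading, six affected at one dose and one at the other give 7/12 = 58.3%, which does not meet the rule. When 8 of 12 is met, the total does not show which dose is intolerable.

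The 50% maximum is tied to a completed cohort of planned size. As an illustration of an assumed shortfall, 6 evaluable patients at the judged dose and 4 at the other would give 6/10 = 60%, which meets the threshold.

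**The case against.** **The within-dose reading is the natural one.** Criterion (1) speaks of events at a dose, which already points to the patients given that dose. The preceding sentence applies the criteria cohort by cohort, and criterion (2) uses the cohort phrase only to set scope. The 50% maximum arises only if the numerator is confined to one dose while the denominator spans both, and no section states that combination. This objection largely stands: the text favours 4 of 6. What remains is that the base is not stated. In criterion (2), a count of one patient, the base does not matter; in criterion (1), a percentage, it decides the result.

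**A reader might go further and infer that the stopping rule can never be met, or that safety oversight is inoperative.** The documents do not support that. The favoured reading is reachable, criterion (2) is unaffected, PK and safety data are evaluated before escalation within a cohort, and the DSMB reviews safety. The DSMB Charter is not among the documents and may state the base.

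**The Section 5.1.1 slip has little operational effect.** Its count of six agrees with the Synopsis and Section 3.1.2, and a missing split is less detail rather than a contrary instruction. Followed together, the sections give one answer for opening Cohorts 2 to 4. That stands. It does not carry over to Cohort 5: a reader might infer that the three-per-dose condition protects every cohort, but the exception can set it aside, and its extent is unclear. The exception is permissive, and no document shows a decision that has turned on 3 versus 6.

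**The counts assume exactly 6 evaluable patients per dose.** Correct. Section 11.10 allows the sample size to grow, and Sections 3.1.1 and 4.2.3 make replacement optional and exclude dropouts due to adverse events.

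**Conclusion.** The two parts have different strength.

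(a) Section 5.1.1 is wrong as written. Six patients are 100% of a planned dose group and 50% of an age cohort, and the section omits the dose split required elsewhere. The Cohort 5 exception inherits the unit, so the waived share is 3 of 6 or 6 of 12.

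(b) Criterion (1) in Section 3.1.6 is a decision threshold with an inconsistent base; it is not shown to be unreachable. The plausible trigger is 4 of 6 at the dose judged. The literal cohort base caps one dose at 50%, so four to six affected patients meet the rule on one reading and do not on the other.

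These results rest on the planned 6 + 6 evaluable patients and on nothing else. Confidence is high about the wording. The practical effect cannot be judged without the DSMB Charter. Because these are safety thresholds and the correction is cheap, it should be made.

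**What to change.** - Reconcile Section 3.1.6 with Section 3.1.1 so that the numerator, the denominator and the dose being judged refer to the same stated patients. Say whether planned or currently evaluable patients form the base.
- Reconcile Section 5.1.1, and the Cohort 5 exception in the Synopsis and Sections 3.1.2 and 5.1.1, with the cohort-opening conditions in the Synopsis and Section 3.1.2 on unit, number and dose split.
- Check that the DSMB Charter uses the same definitions.

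Which rule applies is for the sponsor and DSMB; this point asks only that the passages agree. The cost is wording in four places (Synopsis, Sections 3.1.2, 3.1.6 and 5.1.1) and a Charter check. Sample size and study procedures do not change.

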3.1.7. Steering Committee

A steering committee consisting of a panel of study Investigators or therapeutic area experts will be convened to provide clinical and scientific expertise to Daiichi-Sankyo on the design, execution, and analysis of this Phase 1 pediatric study. Responsibilities of the Steering Committee are set forth in the Steering Committee Charter.

3.2. Selection of Doses

3.2.1. Experimental Treatments

Not applicable.

3.2.1.1. For the Study

Edoxaban will be evaluated in all patients in 1 treatment period. Each patient will receive a single oral dose on Day 1. In each age cohort, appropriated doses will be selected to achieve exposures comparable to adult doses of 30 mg (low-dose groups) and 60 mg (high-dose groups). The doses given to each age cohort and dose group will be adjusted based on emerging data.

3.2.1.2. For Individual Patients

The dose given to individual patients will be based on age cohort, body weight and targeted exposure as described in Section [3.2.1.1](#).

3.2.2. Control Treatments

Not applicable.

4. STUDY POPULATION

4.1. Enrollment

The Investigator will maintain a confidential screening log of all potential study candidates that includes limited information of the patients (initials, age [derived], and sex), date, and outcome of the screening process (e.g., enroll in the study, reason for ineligibility, and refused to participate).

The Investigator will be expected to maintain an enrollment log of all patients enrolled in the study indicating their assigned study number.

The Investigator will maintain a confidential patient identification code list. This confidential list of names of all patients allocated to study numbers on enrolling in the study allows the Investigator to reveal the identity of any patient, when necessary.

Patients will be considered enrolled upon obtaining informed consent (assent, when applicable) at randomization.

Each patient or legally acceptable representative will sign an ICF and assent, if applicable, as required by country-specific regulatory authorities. For additional information on informed consent, see Section [1.6.2](#).

4.1.1. Inclusion Criteria

Male and female pediatric patients who may require or are currently on anticoagulant therapy may be enrolled.

These may include:

- Patients who have a recently acquired or Investigator determined ongoing risk of thromboembolic events (e.g., patients with thrombophilia, congenital heart disease, presence of a central venous catheter and prior VTE).
- Patients who are completing their standard-of-care anticoagulant therapy. Edoxaban can be initiated 12 hours after cessation of enoxaparin, dabigatran, or apixaban therapy (A-U136, A-U151, and A-E152) and 24 hours after cessation of rivaroxaban therapy (A-U151). Note: that the dose of edoxaban should be at the time of the next scheduled standard-of-care anticoagulant administration:
 - At least 4 hours after last dose of unfractionated heparin.
 - At least 12 hours after last dose of bid LMWH.
 - At least 24 hours after last dose of qd LMWH and SP Xa inhibitors.
 - For patients who were on a prior vitamin K antagonist (e.g., warfarin [C-U122] and any other anticoagulants) therapy, INR value should be ≤ 2.5 prior to edoxaban dosing. If the patient's INR is > 2.5 , the patient's INR should be monitored until it is ≤ 2.5 .

- Patients who are currently treated for VTE with at least 5 days of heparin may interrupt their standard-of-care anticoagulant therapy for edoxaban administration. The dose of edoxaban should be:
 - At least 12 hours from last dose of bid LMWH, with a restart of LMWH 24 hours after edoxaban dose.
 - At least 24 hours from last dose of qd LMWH, with a restart of LMWH 24 hours after edoxaban dose.
- Patients with cardiac conditions who may require anticoagulant therapy.
- Patients with sickle cell disease who may require anticoagulant therapy.

For any condition, anticoagulant treatment interruption or discontinuation should not take place if the patient is at increased risk and should be appropriate as per standard-of-care practices.

Patients must satisfy all of the following criteria to be included in the study. Any temporal changes in the following criteria that may prohibit patient consideration, but should normalize for future eligibility, should be reassessed for the patient's future participation in the study:

1. Patients/legal guardian(s) must be able to provide written informed assent (patient, when applicable) and ICFs (signed by parent/legal guardian) prior to participating in the study.
2. Male or female patients 38 weeks gestation to < 18 years of age on the day of dosing.
3. Patients 2 to < 18 years of age must have a body mass index (BMI) between the 5th and 95th percentile based on the 2000 CDC Growth Charts⁷ (the maximum number of patients in each dose group that have a BMI between the 85th and 95th percentile should not be more than 2 patients). Patients < 2 years of age must have a body weight between the 5th and 90th percentile based on the 2000 CDC Growth Charts.⁷
4. Female patients who have had menarche must test negative for pregnancy, as per local practice, at screening and check-in.
5. Female patients who have had menarche and are sexually active must agree to use an effective contraception method, per local practice, for at least 30 days prior to edoxaban dose.
6. Patients/legal guardian(s) must agree to food and drug restrictions during the study.
 - Patients must agree to abstain from and/or legal guardians must agree not to give the patient cola, tea, coffee, chocolate, and other caffeinated drinks and food from 48 hours before dose administration to until after the last PK sample collection (see Section 5.3 for a complete list). Mothers who are breastfeeding study patients should maintain this same dietary restriction for 24 hours prior to edoxaban dosing.
 - Patients must agree to abstain from and/or legal guardian(s) must agree not to give the patient St. John's Wort and food/supplement and beverages containing grapefruit, grapefruit juice, and Seville oranges from 14 days before the first dose through to until after the last PK sample collection (see Section 5.3).

- Patients must agree to abstain from CYP3A4 inhibitors/inducers and P-gp inhibitors/inducers for 14 days prior to the edoxaban dose to until after the last PK sample collection (see Section 5.2).
7. Patients must agree to abstain from the use of nonsteroidal anti-inflammatory drugs (such as ibuprofen) and antiplatelet (except for low-dose aspirin) from 14 days prior to edoxaban dose until after the last PK sample is collected. Patients on low-dose aspirin treatment (1 to 5 mg/kg/day, maximum of 100 mg/day) are permitted to participate in the study per the Investigator's judgment that this does not place the patients at risk. Low-dose aspirin on Day 1 should be withheld until 4 hours post edoxaban dose.
8. Other than signs and symptoms characteristic to their disease state, patients are to be in good health as determined by the absence of clinically significant deviations from normal, with respect to medical and surgical history, physical examination, vital signs, and laboratory reports, as deemed by the Investigator prior to enrollment.

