Switching to edoxaban from other drugs has been studied in healthy adults. Edoxaban can be initiated 12 hours after cessation of enoxaparin, dabigatran, or apixaban therapy (A-U136, A-U151, and A-E152) and 24 hours after cessation of warfarin or rivaroxaban therapy (C-U122 and A-U151).

The PD responses, specifically activated aPTT, PT, and anti-FXa activity, closely parallel the time course of plasma edoxaban concentrations. On the basis of these biomarkers and others measuring thrombin generation, the onset of action for the anticoagulant effects of edoxaban is observed immediately after the first dose and maximum activity corresponds with maximum concentration (C_{max}).

Clinical (90 mg) and supra-therapeutic (180 mg) doses of edoxaban had no effect upon QT_{cI} interval in the thorough QT_c study, which was confirmed to have adequate sensitivity based on the QT_{cI} effect of the positive control (moxifloxacin 400 mg). Moreover, QT_{cF} and QT_{cB} methods yielded the same conclusion. Systemic exposure (as defined by C_{max} and area under the concentration-time curve [AUC] parameters) to edoxaban and its metabolite D21-2393 from the 90 mg edoxaban dose was consistent with results from previous studies.

Beriplex P/N, a 4-factor prothrombin complex concentrate has been evaluated as a potential reversal agent in a study in healthy volunteers. In this study, bleeding duration (BD) prolongation after a punch biopsy was the primary end point. Beriplex P/N dose-dependently reversed the effects of edoxaban on BD. Complete reversal was observed following 50 IU/kg dose, partial reversal was observed following 25 IU/kg and no reversal was observed following 10 IU/kg. This treatment, however, has not been tested in patient populations with bleeding.

Details of these and additional clinical studies are provided in the Investigator's Brochure.¹

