1.5. Population, Route, Dosage, Dosage Regimen, and Treatment Period

The study population will include patients 38 weeks gestation to < 18 years of age of both sexes, who may require, or are currently on anticoagulant therapy.

These may include:

- Patients who have a recently acquired or Investigator determined ongoing risk of thromboembolic events (e.g., patients with thrombophilia, congenital heart disease, presence of a central venous catheter and prior venous thromboembolic event [VTE]).
- Patients who are completing their standard-of-care anticoagulant therapy. Note: that the dose of edoxaban should be at the time of the next scheduled standard-of-care anticoagulant administration:
 - At least 4 hours after last dose of unfractionated heparin.
 - At least 12 hours after last dose of bid low molecular weight heparin (LMWH).
 - At least 24 hours after last dose of qd LMWH and synthetic pentasaccharide (SP) Xa inhibitors.
 - For patients who were on a prior vitamin K antagonist (e.g., warfarin [C-U122] and any other anticoagulants) therapy, international normalization ratio (INR) value should be ≤ 2.5 prior to edoxaban dosing. If the patient's INR is > 2.5 , the patient's INR should be monitored until it is ≤ 2.5 .
- Patients who are currently treated for VTE with at least 5 days of heparin may interrupt their standard-of-care anticoagulant therapy for edoxaban administration. The dose of edoxaban should be:
 - At least 12 hours from last dose of bid LMWH, with a restart of LMWH 24 hours after edoxaban dose.
 - At least 24 hours from last dose of qd LMWH, with a restart of LMWH 24 hours after edoxaban dose.
- Patients with cardiac conditions who may require anticoagulant therapy.
- Patients with sickle cell disease who may require anticoagulant therapy.

For any condition, anticoagulant treatment interruption or discontinuation should not take place if the patient is at increased risk and should be appropriate as per standard care of practices.

The following dosage forms will be provided for this study:

- Edoxaban 30 mg oral tablets for patients 12 and < 18 years of age.
- Edoxaban granules for oral suspension (60 mg reconstituted with 8-mL water) to provide a 6 mg/mL suspension for oral administration for patients < 12 years of age.

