4.2.4. Patient Re-screening

Re-screening of patients that fail to meet the Inclusion and Exclusion criteria is allowed if the reason for failure to meet the criteria has resolved and is no longer considered a risk to the patient (e.g., temporal laboratory deviations meeting exclusion criteria, treatment with contraindicated medications, non-chronic diagnoses). Re-screening of patients for this reason will be reviewed on a case-by-case basis and is dependent upon approval from the Medpace and Daiichi Sankyo Medical Monitors. However, if a patient is screened but cannot dose for

personal/logistic reasons within 21 days of screening, they will need to be re-screened. The exception is, patients that were previously on warfarin therapy and need to be within the acceptable range of INR values. This will not be considered rescreening, and only INR values will be monitored at subsequent testing to ensure that prior to edoxaban dosing, the patient meets inclusion with $\text{INR} \leq 2.5$.

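### For once-daily enoxaparin the eligibility text gives two minimum intervals before edoxaban, 12 h and 24 h, without saying which governs; the scope of the INR clause is also unclear

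*Combined protocol and SAP*

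**What the plan says.** For patients completing standard-of-care anticoagulation, Section 4.1.1 opens with a general statement: "Edoxaban can be initiated 12 hours after cessation of enoxaparin, dabigatran, or apixaban therapy (A-U136, A-U151, and A-E152"). It gives 24 h for rivaroxaban. The synopsis repeats this. Neither place names an enoxaparin regimen.

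A note follows directly: "the dose of edoxaban should be at the time of the next scheduled standard-of-care anticoagulant administration". Its sub-items include "At least 12 hours after last dose of bid LMWH" and "At least 24 hours after last dose of qd LMWH and SP Xa inhibitors".

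Section 1.5 describes the same population with the note and the sub-items, including "At least 24 hours after last dose of qd LMWH and synthetic pentasaccharide (SP) Xa inhibitors", but without the opening statement.

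The last sub-item in all three places sets an INR ceiling of 2.5. Its scope reads "For patients who were on a prior vitamin K antagonist (e.g., warfarin [C-U122] and any other anticoagulants) therapy". Section 4.2.4 applies the repeat-INR procedure to "patients that were previously on warfarin therapy and need to be within the acceptable range of INR values".

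Section 1.1.1.5, which summarises switching studies in healthy adults, also mentions "24 hours after cessation of warfarin or rivaroxaban therapy (C-U122 and A-U151").

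**The concern.** A site with a once-daily enoxaparin patient can find support in one paragraph for dosing at 12 h and for waiting at least 24 h. Section 6.5 allows no deviation or waiver except to remove an immediate hazard, so the rule has to be unambiguous if a monitor is to classify such a case.

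Two things are at stake. The first is safety: anticoagulant left from the previous therapy overlaps with edoxaban in the hours after dosing. The second is the secondary PD endpoints (PT, aPTT, anti-FXa), which respond to residual anticoagulant as well as to edoxaban. Section 11.1.2 makes the PD analysis set depend on dosing in line with the protocol and on the absence of compromising deviations. Where the text gives two intervals, membership of that set is not clearly defined for these patients.

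**Working it through.** There is no plan figure to reproduce. The check sets the passages side by side.

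| Prior therapy | Synopsis and 4.1.1 | Section 1.5 | Result |
|---|---|---|---|
| Enoxaparin, twice daily | 12 h (opening statement); at least 12 h (sub-item) | at least 12 h | Consistent |
| Enoxaparin, once daily | 12 h (opening statement); at least 24 h (sub-item) | at least 24 h | Two minimum intervals |
| Dabigatran, apixaban | 12 h | no hour figure | Rule missing from 1.5 |
| Rivaroxaban | 24 h | no hour figure | Rule missing from 1.5 |
| Warfarin | INR ≤ 2.5 | INR ≤ 2.5 | Consistent; 4.2.4 agrees |

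**Enoxaparin.** The conflict is confined to once-daily use, where the two minimum intervals differ by 24 − 12 = 12 h. The opening statement cannot be set aside as background. It is the only place in the criteria with an hour-based rule for dabigatran, apixaban and rivaroxaban, so it has to be operative, and enoxaparin stands in the same clause.

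**INR clause.** The governing term is vitamin K antagonist, but the parenthesis adds other anticoagulants. Read literally, this brings drugs that already have an hour-based rule under an INR ceiling too. Section 4.2.4 names warfarin alone.

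**Where residual activity would be seen.** Under Section 8.2.1, Cohorts 1 to 3 have a predose PD sample, which captures residual effect at dosing but not its later decline. Cohorts 4 and 5 have one PD sample at screening (Days −21 to −2, Section 6.1) and one at 0.5 to 2 h postdose. Residual anti-FXa activity at dosing is therefore not measured in them, and change from baseline cannot separate it from the edoxaban effect. Footnote 6 of Table 17.1 lets the single pre-dose safety coagulation test fall at check-in, but that test covers PT, INR and aPTT, not anti-FXa. Section 11.5.2 has no breakdown by background anticoagulant.

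**Possible size.** Assume first-order decline with half-life h, so that the residual fraction is 2^(−t/h). The range h = 3 to 7 h is an assumption; the documents give no value.

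- At 12 h: 2^(−12/3) = 6.25%; 2^(−12/7) = 30.5%.
- At 24 h: 2^(−24/3) = 0.39%; 2^(−24/7) = 9.3%.
- Ratio, 2^(12/h): 16 for h = 3 h; 3.3 for h = 7 h.
- Absolute gap: 6.25 − 0.39 = 5.9 percentage points for h = 3 h; 30.5 − 9.3 = 21.2 points for h = 7 h.

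The largest ratio goes with the smallest absolute gap, so neither should be quoted alone. One affected patient would be 1/6 = 17% of a dose group.

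**The case against.** The strongest reply is that the note already settles the matter. The opening statement is permissive and cites studies. The note then ties dosing to the next scheduled anticoagulant administration and separates twice-daily from once-daily LMWH. Section 1.5 and the separate item for patients under treatment for VTE use the same split without the 12 h statement. A patient dosed at or after 24 h satisfies every passage. This is a reasonable reading and it narrows the problem, but the text does not say that the note overrides the statement.

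On the INR clause, the reply is that the added words only give examples of vitamin K antagonists, and that an hour minimum and an INR ceiling can both be met. That stands: the clause is unclear in scope, but it does not contradict the hour-based rules.

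Four stronger readings are tempting, and the documents do not support them.

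- A reader might infer that warfarin also has two competing rules. The 24 h figure appears only in the background summary in Section 1.1.1.5. The synopsis and Sections 1.5, 4.1.1 and 4.2.4 all use INR ≤ 2.5, so a warfarin patient dosed at 24 h with a higher INR fails the criteria.
- A reader might infer that early-dosed patients all count as compliant and pass unnoticed. Dosing once-daily enoxaparin at 12 h fails the 24 h sub-item. Medication history is taken at screening and check-in (Sections 6.1 and 6.3.2), and prior medications are tabulated (Section 11.3). What is not specified is recording the time of the last anticoagulant dose.
- A reader might infer that the mix of intervals will differ between dose groups. That is possible in a non-randomised study, but nothing in the documents shows it.
- A reader might infer harm to the primary objective. Edoxaban is measured by LC-MS/MS (Section 8.1.2), and residual heparin would not be expected to change that measurement.

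The bar on interrupting therapy in patients at increased risk, and exclusion criteria 5 and 18, also limit the safety exposure.

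**Conclusion.** The concern holds in a narrow form. For once-daily enoxaparin only, the synopsis and Section 4.1.1 give two minimum intervals, 12 h and at least 24 h, and do not state which takes precedence. Section 1.5 carries a different rule set, and the reach of the INR clause is unclear. These are wording conflicts in an operative eligibility and dosing rule. Which interval is right is not judged here.

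The consequences fall on safety at dosing and on descriptive secondary PD results, chiefly in Cohorts 4 and 5. How many patients are affected cannot be told from the documents and could be none. Any residual-activity figure depends wholly on the assumed half-life. The point merits correction because the passages cannot all guide a site as they stand and the correction is cheap.

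**What to change.** - Reconcile the synopsis, Section 1.5 and Section 4.1.1 so that each agent and regimen has one criterion, stated identically in all three places; a single table would do this. The sponsor decides which value stands.
- State which agents the INR clause covers, and make Section 4.2.4 agree. Mark the switching summary in Section 1.1.1.5 as background.
- Record the agent, regimen, and date and time of the last anticoagulant dose on the CRF.
- Treat dosing outside the reconciled rule as a deviation to be assessed for the PD analysis set.

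Cost: a wording amendment and a few CRF fields, with no additional patients, visits or samples.
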